## ABBREVIATIONS

ADL	Activities of Daily Living
AGA	Androgenic Alopecia
ADRC	Adipose-Derived Regenerative Cells
AE	Adverse Event
ANC	Absolute neutrophil count
ANCOVA	Analysis of covariance
AFT	Autologous Fat Transfer
CFU-F	Colony Forming Units Fibroblast
CFR	Code of Federal Regulations
DMC	Data Monitoring Committee
eCRF	Electronic Case Report Form
ET	Early Termination
FPHL	Female Pattern Hair Loss
FDA	Food and Drug Administration
GCP	Good Clinical Practice
ICH	International Conference on Harmonization
ID	Identification
IFU	Instructions for Use
IV	Intravenous
IDE	Investigational Device Exemption
IND	Investigational New Drug
IRB	Institutional Review Board
ITT	Intent-to-Treat
IVRS	Interactive Voice Response System
IWRS	Interactive Web Response System
MPHL	Male Pattern Hair Loss
PI	Principal Investigator
pRBC	Pack Red Blood Cells
PTE	Per Treatment Evaluation
RBC	Red Blood Cell
SAE	Serious Adverse Event
SAP	Statistical Analysis Plan
SD	Standard Deviation
WBC	White Blood Cell

## 1 OBJECTIVE

The primary objective of this study is to evaluate the safety and efficacy of the Cytori Celution and Puregraft Systems in the processing and preparation of an autologous fat graft enriched with adipose-derived regenerative cells (ADRCs) in the treatment of early alopecia androgenetica.

## 2 BACKGROUND

### 2.1 Alopecia Androgenetica

Alopecia Androgenetica (AGA) is the most common form of both male pattern hair loss (MPHL) and female pattern hair loss (FPHL) with the condition affecting approximately 50% of the male population and less than 45% of women going through life with a full head of hair. The degree of hair loss in the male patient is generally classified using the Norwood Hamilton Classification (Figure 1) and FPHL is evaluated based on the Savin scale (Figure 2). The incidence and prevalence of the condition are generally well documented in both genders. Stough and co-workers reported that in White males, 30% have AGA by age 30 and 50% by age 50 with lower incidences seen in African American, Chinese, and Japanese populations. In a population based report looking at MPHL, the authors reported that in the 30-35 years age group, grade I hair loss was 51%, while grade II was 43% and grade VI was only approximately 19%--clearly highlighting early hair loss in the younger population. Of the 1,005 men in the study aging from 30-50 years, 44% were found to have grades I-III hair loss.

In women, diffuse thinning and loss of hair density with maintenance of the frontal hairline describe the typical pattern of loss. In one report, the prevalence of early, clinically detectable FPHL was 12% of females between 20-29 years of age and 25% by 49 years of age. In the table presented below (Table 1), Gan and Sinclair documented the distribution of hair loss in 752 women using a modified 5-point grading scale. Below the age of 40 years, 99% of women reporting loss documented early stage loss.

[figure not shown]
Table IV. Hair patterns in female subjects

Age	Hair thickness					Total	1-stage 1
	Stage 1	Stage 2	Stage 3	Stage 4	Stage 5		
5-9	72 (100%)						—
20-29	50 (88%)	5 (9%)	1 (2%)	1 (2%)		57	7 (12.3%)
30-39	73 (83%)	14 (16%)		1 (1%)		88	15 (17.0%)
40-49	91 (75%)	28 (23%)		3 (2%)		122	31 (25.4%)
50-59	106 (72%)	29 (20%)	11 (7%)	1 (1%)		147	41 (27.9%)
60-69	73 (59%)	37 (30%)	11 (9%)	2 (2%)	1 (1%)	124	51 (41.1%)
70-79	58 (46%)	35 (28%)	24 (19%)	6 (5%)	2 (2%)	125	67 (53.6%)
≥ 80	23 (43%)	15 (28%)	8 (15%)	8 (15%)		54	35 (57.4%)
Total	474 (66%)	163 (23%)	55 (8%)	22 (3%)	3 (0.4%)	717	247 (32.2% a )

aAdjusted to age.

In sum, a significant percentage of both male and female population suffer from AG at a relatively early age.

Figure 1—MPHL Norwood Hamilton Classification

**Class I** represents an adolescent or juvenile hairline and it not actually balding. The adolescent hairline generally rests on the upper brow crease.

**Class II** indicates a progression to the adult or mature hairline which sits a finger breath (1.5cm) above the upper brow crease, with some temporal recession. This also does not represent balding.

**Class III** is the earliest stage of male hair loss. It is characterized by a deepening temporal recession.

[figure not shown]
**Class III Vertex** represents early hair loss in the crown (vertex).

**Class IV** is characterized by further frontal hair loss and enlargement of vertex, but there is still a solid band of hair across top separating front and vertex.

**Class V** the bald areas in the front and crown continue to enlarge and the bridge of hair separating the two areas begins to break down.

**Class VI** occurs when the connecting bridge of hair disappears leaving a single large bald area on the front and top of the scalp. The hair on the sides of the scalp remains relatively high.

Figure 2—FPHL Ludwig Scale

The current treatment regimen for alopecia androgenetica is a spectrum ranging from non-invasive medicinal approaches to robot-assisted surgical transplantation of thousands of follicular units. On the non-invasive side, the two medicines currently approved for treatment of genetic pattern alopecia by the FDA are finasteride (for men only) and minoxidil. Both of these medicines carry untoward side-effects. For finasteride, sexual dysfunction, particularly for the younger patient who is most likely to present with early hair loss, was seen in between 2.1% and 3.8% of men. Initial treatment of early alopecia is typically non-invasive and the two medications approved by the FDA today are minoxidil and finasteride. For minoxidil, it is reported that approximately one-third of patients with AA respond with new hair growth. In contrast, invasive transplant options are generally not offered to patients with early AA and if so, require significant financial resources. As a result, there remains a significantly large gap between these medicinal and transplant options. Hence a distinct medical need remains specific to addressing early alopecia.

During hair follicle growth (anagen), the hair follicle delves deep into the rich dermal macroenvironment as it grows to maturity where it is surrounded by large lipid-filled adipocytes. These intradermal adipocytes regenerate with faster kinetics than other adipose tissue depots and such growth parallels with the hair cycle, suggesting an interplay exists between hair follicle cells and adipocytes. Thus, it has been established that adipose is an integral part of the normal hair cycle and it is hypothesized that telogen may be due to an absence of adipose tissue as it is reported that hair loss and decreased adipocytes occur together. Therefore, the transplantation of adipose tissue, or autologous fat transfer (AFT), into the subcutaneous layer of fat in the scalp for purposes of stimulating hair growth is consistent with the reported literature that indicates hair loss and adipose loss occur in tandem.

### Autologous Fat Transfer

In an AFT procedure, a patient's subcutaneous adipose tissue is aspirated from one location (most commonly the abdomen or thighs) and transferred into another depot of subcutaneous fat located throughout the body (e.g., mid-face). This procedure is reported to be practiced by physicians for over 100 years and autologous fat should be free from problems often associated with artificial materials or from allergic reactions. However, AFT is not without its own limitations most significant of which is the fact that an unpredictable amount of the transferred fat can die as a result of damage during tissue harvest, processing, and implantation leading to loss of volume and a degree of unpredictability in outcome.

The process of fat transfer necessarily involves disconnecting the fat from its blood supply, implanting it into the defect, and then waiting for natural healing processes to incorporate the transferred tissue with native fat. Survival of the transferred tissue is dependent upon harvest and processing approaches that maximize tissue viability. It is also dependent upon simple diffusion to supply nutrients and oxygen and to remove wastes until such time as healing processes restore its blood supply. Diffusion through a solid tissue such as fat is only effective across a distance of a few millimeters. Consequently, any transferred tissue that is more than a few millimeters away from the blood supply of recipient site tissue is at risk of dying. Loss of graft tissue from this problem is a frequent problem. Clinicians frequently overcorrect adding extra tissue in an effort to compensate for inevitable tissue loss that has been estimated at between 20-80% of the implanted tissue. As a result of this unpredictability defect repair frequently requires multiple repeated or staged procedures performed at intervals of three or more months. For example, one large study reports up to five treatments needed (mean = three treatments) in order to achieve success in restoring volume. This leads to delays in achievement of effective treatment of the defect, expense, and the higher morbidity of repeated tissue collection and implantation.

A number of investigators have evaluated ways by which the healing process can be modulated in an effort to understand and augment graft retention and, thereby, limit the number of procedures needed to achieve successful treatment. For example, animal studies have shown that use of agents that stimulate the healing process (for example, gene therapy with factors that stimulate new blood vessel growth) can increase the survival of transferred tissue and that, conversely, agents that inhibit healing reduce survival. Recent preclinical and clinical data have shown in addition to being a source of tissue for soft tissue filling, human adipose tissue contains cells that have the ability to promote healing. Zhu *et al* have used an animal model to show that coating one volume of adipose tissue with cells isolated from another volume of adipose tissue results in an approximate doubling of graft retention at six and nine months. This finding has been confirmed by an independent study. The concept of this approach is that signals generated at the interface between implanted fat and adjacent breast fat will induce improved healing. Increasing the number of cells capable of generating these signals at this interface will lead to successful tissue retention.

In addition, Puregraft processed adipose has an excellent safety profile in aesthetic body contouring.

Currently, there are few, if any, minimally invasive, autologous cell therapeutic modalities being developed that address early alopecia. However, analyses from other therapeutic applications of

ADRCs and AFT suggest that a cell-enriched based approach for the treatment of early alopecia may be of significant benefit.

### ***2.1.1 Clinical Experience with ADRCs***

To date, thousands of patients have been treated with autologous ADRCs isolated using the Celution System (Cytori Therapeutics, San Diego, USA). Celution processed ADRCs have an excellent safety profile in a variety of conditions including acute myocardial injury, patients with chronic heart muscle damage, breast insufficiency following lumpectomy (a cell-enriched AFT procedure), chronic cutaneous wounds, and urinary incontinence, and most recently in a small study of scleroderma patients.

In addition, Puregraft processed adipose has an excellent safety profile in aesthetic body contouring.

Cytori's initial clinical experience in treating pathological conditions was in the myocardium. The PRECISE Clinical Trial evaluated the safety and feasibility of intramyocardial administration of ADRCs in patients with chronic myocardial ischemia not amenable to revascularization. Clinical results at 18 months have demonstrated safety and signs of feasibility. PRECISE was a prospective, double-blind, randomized, parallel group, placebo-controlled, sequential dose escalation study which enrolled 27 subjects. Following baseline electromechanical mapping, subjects received  $\leq 15$  intramyocardial injections of ADRCs (n=21; median dose of ADRCs  $42 \times 10^6$  per subject) or placebo (n=6: indistinguishable solution) in the area(s) of the heart with inducible ischemia. ADRCs were processed using the Cytori Celution System. ADRC-treated subjects demonstrated improvement in maximum oxygen consumption ( $VO_2\text{max}$ ) relative to a placebo control. Adverse events and serious adverse events were equally distributed across all treatments groups with angina reported as the most frequent SAE.

The APOLLO Clinical Trial was a safety and feasibility study of ADRCs processed by the Celution System and delivered via the intracoronary route in the treatment of patients with ST-segment elevation myocardial infarction (STEMI). This was a prospective, double-blind, 3:1 randomized (ADRC: Placebo), parallel group, placebo-controlled trial. A total of 14 patients were enrolled and treated according to protocol, 10 patients received ADRCs and four received placebo.

The APOLLO study demonstrated that liposuction adipose harvest for the purpose of processing and returning autologous ADRCs via the intracoronary infusion of  $20 \times 10^6$  ADRCs can be performed with an acceptable safety profile.

Case series have described benefits in the treatment of radiation injury, fistulas and stress urinary incontinence. Yoshimoto et al. described efficacy of ADRC treatment in three patients presenting with chronic radiation injuries with ulcers and severe fibrosis. They reported increases in local blood circulation at the site by ultrasound and dramatic wound healing. Gotoh et al recently described improvements in urinary incontinence following ADRC injections in a case series of 11 men who underwent radical prostatectomy. Of note, enhanced ultrasonography showed a progressive increase in blood flow to the injected area in all patients. Borowski reported complete wound closure of three patients treated for long-standing cryptoglandular fistula-in-ano

using ADRCs. An open label trial in 12 patients with systemic scleroderma from France examining the effects of subcutaneous administration of ADRCs to all fingers has recently been published. Data at six months indicated significant improvements in Cochin score, Raynaud's severity score, and in the Scleroderma Health Assessment Questionnaire (SHAQ). The procedure was tolerated well without complications.

### 3 RATIONALE

For both sexes, the negative physical and psychological effects of AGA have been documented. In Stough's report, the authors indicate that while the condition may not appear to cause direct physical harm in men, hair loss can protect against sunburn, cold temperatures, mechanical injury, and ultraviolet light. Beyond the physical, hair loss is known to psychologically affect the balding individual's perceptions of themselves. This is particularly true when looking at FPHL, where Cash and co-workers reported that while AA was a stressful experience for both sexes, it was substantially more distressing for women. In sum, the impact of the condition should not be relegated as simply aesthetic in nature, and therefore satisfactory treatment regimens are necessary.

### 4 STUDY DESIGN

The STYLE Trial is a prospective, randomized, multi-center device trial intended to evaluate the safety and efficacy of the Celution and Puregraft Systems in the processing and preparation of an autologous fat graft enriched with adipose-derived regenerative cells (ADRCs) in the treatment of early alopecia androgenetica. Patients may be included if they are undergoing an elective cosmetic liposuction. Following informed consent and screening evaluations, eligible subjects will undergo pre-operative testing. Subjects will then undergo a fat harvest using local anesthesia with or without conscious sedating. Subjects will be randomly assigned to receive a fat graft cell enriched with ADRCs (available in two different doses), a fat graft without cell enrichment using a visually-matched blood saline solution (fat alone control), or a saline injection (no-fat control) in a 2:2:2:1 ratio.

While undergoing liposuction, lipoaspirate will be processed in the Puregraft System to remove the lipoaspirate of impurities and in the Celution System to isolate and concentrate ADRCs. After the liposuction is completed, patients will have, under a ring block local anesthesia (see further description below), a subcutaneous scalp injection of either Puregraft purified autologous fat or saline (no-fat control) followed by a separate second injection, of either ADRCs (available in two different doses), a visually-matched blood saline solution (fat alone control), or saline (no-fat control) in a 2:2:2:1 ratio.

All subjects will undergo clinical evaluations and laboratory testing prior to and after the procedure as outlined in *Section 9.0, Study Assessments*, and in the *Schedule of Procedures (Appendix A)*.

## **4.1 Study Population**

Subjects with documented early stage alopecia androgenetica will be evaluated for this study.

## **4.2 Sample Size**

The STYLE Clinical Trial will have a sample size of 70 patients.

## **4.3 Clinical Sites**

Up to eight (8) clinical centers in the United States will be selected to participate in the STYLE Clinical Trial.

## **4.4 Study Duration**

Enrollment of subjects will occur over approximately 6 months. For each patient, the study duration will include a screening period of up to 28 days and a 52 week follow-up period. Therefore, the study duration is estimated to be 18 months.

## **4.5 Study Endpoints**

### ***4.5.1 Primary Endpoint***

Safety & tolerability throughout 24 weeks

### ***4.5.2 Secondary Endpoints***

1. Trichograms (Hair Growth) at 24 weeks (change from baseline)
2. Trichograms (Hair Density) at 24 weeks (change from baseline)
3. Global photographs at 24 weeks (change from baseline)
4. Hair Investigator Satisfaction Survey at 24 weeks (change from baseline)

### ***4.5.3 Exploratory Endpoints***

1. Trichograms (Hair Growth) at times other than 24 weeks
2. Trichograms (Hair Density) at times other than 24 weeks
3. Trichograms (Anagen/Telogen Rate, Hair Thickness) at times other than 24 weeks
4. Global photographs other than 24 weeks
5. Hair Investigator Satisfaction Survey at times other than 24 weeks

### ***4.5.4 Safety Endpoints***

Adverse events, Serious Adverse Events, and UADEs

## **4.6 Inclusion Criteria**

Subjects will be enrolled into this study only if they meet ALL of the following criteria:

1. Males with a diagnosis of Alopecia Androgenetica
2. Females with a diagnosis of Alopecia Androgenetica

3. Males with hair loss consistent with Grades III, IIIA, III-Vertex, IV, IV-A, based on Norwood-Hamilton Scale ([Figure 1](#))
4. Females with hair loss consistent with Grades I-3, I-4, II-1, II-2 based on the Savin Scale ([Figure 2](#))
5. Provide written informed consent and comply with the study requirements
6. For women of childbearing potential: Negative pregnancy test at screening visit plus willingness to maintain two forms of contraception for the duration of the study.
7. Subject is willing to maintain a consistent hair length and natural hair color, including the absence of coloring agents, during the study period.
8. Ability to complete study procedures, patient surveys, and pictures.
9. Subject is  $\geq 18$  years of age.
10. Body Mass Index  $< 40\text{kg}/\text{m}^2$

19. Subject who has a sensitive, irritated, or abraded scalp area.
20. Women who have an alternate diagnosis that is associated with hair loss.
21. Body Mass Index < 18 kg/m^2
22. Clinically significant abnormal findings on laboratory screening panels, including hemoglobin ≤ 10 g/dL.
23. Hepatic dysfunction, as defined as aspartate aminotransferase (AST), alanine aminotransferase (ALT), or bilirubin levels > 1.5 times the upper limit of normal range (x ULN) prior to randomization.
24. Chronic renal insufficiency as defined as a serum creatinine > 1.5 mg/dL in men or > 1.2 mg/dL in women.
25. An elevated PT/PTT, INR, or platelet count < 100 x 10^9/L

## 5 ENROLLMENT

### 5.1 Subject Enrollment

Patients are considered enrolled in this study when all of the following have occurred:

1. Written informed consent is obtained
2. All inclusion criteria and no exclusion criteria have been met
3. All screening evaluations are complete

### 5.2 Randomization and Subject Identification

All subjects will undergo liposuction and will be randomized into one of four parallel arms in a 2:2:2:1 ratio to receive either low dose ADRCs cell enriched fat (n=20), high dose ADRC cell enriched fat (n=20), non-cell enriched autologous fat alone control (n=20), or no-fat control saline injections (n=10). Randomization will be via an interactive voice/web response system (IVRS/IWRS), or an alternatively acceptable system, and occur on the procedure day, prior to the start of liposuction.

Patients randomized into the study will be assigned the treatment corresponding to the next available number in the computer-generated randomization schedule. The dose of the test material (ADRCs or placebo) is discussed in [Section 6.3](#).

Randomization and dose preparation will be performed by an unblinded pharmacist, or other designated qualified personnel, as outlined in the Study Reference Manual. The unblinded pharmacist or designee will not be involved in study patient care, management or follow up procedures and assessments.

### **5.3 Blinding Procedures and Safeguards**

The following will be the “blinded parties”, meaning that the listed will have no knowledge of the patient’s treatment assignment:

- Patients
- Core Laboratories
- Statistician

The “**unblinded parties**”, meaning those that will or may have knowledge of a patient’s treatment assignment, will be the following:-

- Investigators
- Unblinded Pharmacist or designee involved in the dose preparation procedures and randomization of the patient
- Data Monitoring Committee Members

The study blind should not be broken except in a medical emergency (where knowledge of the test material received would affect the treatment of the emergency) or regulatory requirement (e.g., for SAEs or death).

If unblinding becomes necessary, the Investigator should notify the Sponsor or the Medical Monitor as soon as possible. If the blind is broken, the date, time and reason must be recorded in the Subject’s electronic case report form (eCRF), together with a note of a protocol violation if applicable, and any applicable reports [e.g. Adverse Event (AE)].

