## **7.2 Product Description – Control Doses**

The fat alone control dose will be purified autologous tissue prepared by the Puregraft System that is not enriched with ADRCs but with saline. The amount of fat injected will be  $0.1 \text{ mL/cm}^2$  of scalp. The fat alone control dose will also include injection of a saline solution which is mixed with 0.1mL to 0.2 mL of the study Subject's own freshly drawn blood to achieve a dilution that is visually indistinguishable from ADRCs. The saline injection of the fat-alone control must test negative in a Gram stain test of sterility prior to being administered (see [Section 7.3](#)). Preparation of the fat-alone control dose is provided in the *Study Reference Manual*.

The no-fat control dose will be  $0.1 \text{ ml/cm}^2$  of scalp of saline injected (delivered by a blunt tip cannula) followed by a second matching dose of saline solution (via a 25G needle) to  $0.1 \text{ ml/cm}^2$  of scalp.

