## **11 STATISTICAL METHODS AND DATA ANALYSIS**

This is a multi-centre, single-blinded, randomized, parallel group, controlled study to evaluate the preliminary safety of cell-enriched autologous fat compared to placebo in patients with baldness due to alopecia androgenetica. The primary endpoint will be the safety and tolerability of the procedure.

An analysis of covariance (ANCOVA), with the baseline measure used as a covariate, will be used for the analyses of the secondary efficacy endpoints. Comparisons of each active arm with placebo will be made using Dunnett comparisons. The ITT population will be used for the primary analysis; the analysis will also be performed in the PTE population and will be considered as supportive of the ITT analysis.

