## **12.2 Procedures for AE Reporting**

All AEs will be recorded by the investigator or designee on the appropriate electronic case report form (eCRF). Events that occur prior to the liposuction-related activities, including those that are considered serious, are to be recorded in the medical history. Events, including SAEs, which occur after liposuction-related activities are initiated on procedure day, are to be recorded on the AE eCRF. The investigator will evaluate the relationship of the adverse event to both the test material and study procedure as unrelated, unlikely, possibly, probably, or definitely related and will record the findings, including all pertinent details of the event on the eCRF.

In addition, the Investigator or designee will report any serious adverse events, including UADE, occurring during this study to the Sponsor and Medical Monitor as soon as possible, but no later than 24 hours after the Investigator first identifies the adverse event.

The Investigator will take appropriate measures to ensure the subject's well-being and document these measures on the appropriate eCRF.

All serious adverse events experienced will be monitored until the event has resolved, any abnormal laboratory values have returned to baseline or stabilized at a level acceptable to the Investigator and Medical Monitor, or until there is a satisfactory explanation for the changes observed.

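### Section 5.3 lets investigators know the assignment in every arm, although existing masking could blind them to ADRC versus fat alone in 60 of 70 subjects

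*Combined protocol and SAP*

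**What the plan says.** All references are to Protocol Version B, 24 November 2015, unless stated.

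- **Who may know.** Section 5.3 defines the unblinded parties as "meaning those that will or may have knowledge of a patient’s treatment assignment" and puts investigators on that list without restriction by arm. Patients, core laboratories and the statistician are listed as blinded. Section 11 describes a "multi-centre, single-blinded, randomized, parallel group, controlled study".
- **Masking of the product.** Section 7.2 mixes the fat-alone second injection with a little of the subject's own blood "to achieve a dilution that is visually indistinguishable from ADRCs". Section 4 repeats the visual match for the fat-alone control. No tint is stated for the no-fat arm.
- **Separation of staff.** Section 5.2: "Randomization and dose preparation will be performed by an unblinded pharmacist, or other designated qualified personnel". It adds: "The unblinded pharmacist or designee will not be involved in study patient care, management or follow up procedures and assessments".
- **What investigators rate.** Section 4.5.2 lists as its fourth secondary endpoint "Hair Investigator Satisfaction Survey at 24 weeks (change from baseline". Section 12.2 states: "The investigator will evaluate the relationship of the adverse event", both to the test material and to the procedure. Section 11.3 analyses related events separately.
- **Reason given for wider unblinding.** The Summary of Changes says a no-fat treatment cannot feasibly be disguised against a fat-containing one. It gives this to explain why the sponsor, data management and monitors are unblinded, and it relies on blinded reading of photographs as the safeguard.

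**The concern.** The plan already has the two expensive parts of an investigator blind: a control injection that looks like the active one, and a preparer who is walled off from care and assessment. It then allows the people on the other side of that wall to know the arm. The reason given concerns fat versus no fat. It does not explain why an investigator should know whether a fat-grafted subject's second injection held cells or tinted saline.

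ADRC versus fat alone is the contrast that isolates the contribution of the cells. Two investigator judgements feed into it with no blinded rater described: the satisfaction survey and adverse event relatedness. The survey is especially open to expectation. Appendix A schedules it only after the procedure, and the Summary of Changes describes it as reflecting perceived change. It is therefore a retrospective opinion with no baseline measurement behind it.

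**Working it through.** **1. How many subjects could be masked.** The inputs are N = 70 (Section 11.2) and allocation 2:2:2:1 (Section 5.2).

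- Each fat-containing arm: 70 × 2/7 = 20. No-fat arm: 70 × 1/7 = 10. The plan's 20 + 20 + 20 + 10 = 70 is reproduced.
- Fat-containing arms together: 60/70 = 85.7%. No-fat arm: 10/70 = 14.3%.

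**2. What each contrast reveals to the investigator who injects.**

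| Contrast | First injection | Second injection | Can it be masked? |
|---|---|---|---|
| ADRC v fat alone | fat in both | visual match stated (Section 7.2) | Yes, with what is in place |
| Low v high ADRC dose | fat in both | no match described | Only if confirmed to look alike |
| Any fat arm v no fat | fat v saline | no tint stated for no fat | No |

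Appendix C places the second injection, ADRC or saline, at the same point of the procedure day, so the planned timing does not separate the arms.

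**3. Which outcomes are exposed.** Of the four secondary endpoints, the two trichogram measures and the global photographs are protected by blinded core laboratories (Section 5.3). The survey is not. Relatedness is rated by the investigator (Section 12.2).

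**4. Illustration for the survey.** The documents give no size for the bias, so assume that knowing the arm shifts ratings in the ADRC arms by b SD, that the true effect is zero, and that ratings are normal with equal variance. The two-sided level is 0.05 (Section 11.1). The non-centrality is b/√(1/20 + 1/20) = b/0.316, which is 0.632, 0.949 and 1.581 for b = 0.2, 0.3 and 0.5.

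- *Unadjusted t-test, 20 v 20:* 38 df, critical value 2.024. Rejection rate = P(T > 2.024) + P(T < −2.024), with T non-central t.
- *Dunnett, two ADRC arms v fat alone:* 60 − 3 = 57 df, critical value 2.27 (simulated). The per-comparison rate uses the same formula with 2.27. The rate for at least one of two comparisons is simulated.

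| Assumed shift b | Unadjusted, one comparison | Dunnett, one comparison | Dunnett, at least one of two |
|---|---|---|---|
| 0 | 5% | 2.7% | 5% |
| 0.2 SD | 9.5% | 6% | 10% |
| 0.3 SD | 15.2% | 10% | 17% |
| 0.5 SD | 33.8% | 25% | 38% |

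Section 11 plans ANCOVA with the baseline value as covariate. The survey has no baseline in Appendix A, so a comparison of means without that covariate is a fair stand-in.

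**5. Illustration for relatedness.** If knowing the arm raised the share of ADRC subjects counted as having a related event by an assumed 10 or 20 percentage points, that would be 40 × 0.10 = 4 or 40 × 0.20 = 8 extra subjects. The shift could equally go downward.

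**The case against.** The trial openly declares itself single-blinded. It is a safety and feasibility study with no formal power calculation, so some openness is a legitimate choice. Most of the efficacy evidence is also read blind. Both points stand, and they keep this a moderate matter. Neither explains why the ADRC versus fat-alone masking stops at the investigator.

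A reader might infer more than the documents support in four respects.

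- *That every investigator will know every assignment.* The definition covers parties who may know as well as those who will. Section 5.3 also restricts breaking the blind to emergencies or regulatory need and has the investigator then notify the sponsor, which fits poorly with an investigator who already knows. The text permits unblinding but does not establish it. The list may be meant only to acknowledge that whoever injects saline in place of fat will recognise the no-fat arm.
- *That biased relatedness calls contaminate the primary endpoint.* The hypotheses in Section 11.3.1 concern rates of adverse events and of vital sign and physical examination abnormalities, evaluated clinically without a test. Relatedness is a separate analysis in Section 11.3.
- *That dose can be masked as readily as cells versus no cells.* No visual match between the two ADRC doses is described.
- *That masking would be free.* Cell counts and viability decide whether a preparation is acceptable (Section 7.1.1), so those results would have to bypass the investigator, and sites would need training. Preparation details sit in the Study Reference Manual, which is not among the documents.

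The plan also does not say which control is meant by placebo in the Dunnett comparisons. The masked contrast may therefore not be the one tested, and the Dunnett column above assumes fat alone.

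**Conclusion.** The concern holds as an avoidable risk of bias; no bias has been measured. Section 5.3 permits investigators to know the assignment in all arms, while the stated reason reaches only the 10 no-fat subjects. For the other 60 (86%), the plan's own masking would support an investigator blind to ADRC versus fat alone. One of four secondary endpoints and the separate relatedness analysis are exposed.

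The false-positive figures rest wholly on the assumed shifts. For shifts of 0.2 to 0.5 SD, they run from about 6% to 25% per Dunnett comparison, against 2.7% with no shift. They show that a modest rating bias would matter at 20 per arm. They do not show that such a bias will occur, or in which direction. The change is worth making because it is cheap relative to that risk.

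**What to change.** 1. In Section 5.3, list investigators and site raters as blinded to ADRC versus fat alone and as unblinded only to fat versus no fat. Extend this to ADRC dose only if the two dose preparations are confirmed to look alike.
2. Have the unblinded pharmacist or designee hold the cell-release results and release the second injection in syringes of identical appearance. The acceptance criteria themselves are not affected.
3. In the analysis text, label survey and relatedness comparisons with the no-fat arm as open. State which control the Dunnett comparisons use.
4. If the sponsor prefers to keep investigators unblinded, give the reason for the three fat-containing arms and report the survey and relatedness as unblinded ratings.

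**Cost:** rerouting of release results, a wording change and site training. No extra staff are needed, because Section 5.2 already provides the separate preparer. Emergency unblinding is already described in Section 5.3.
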